## 4 STATISTICAL ANALYSES

### 4.1 GENERAL CONSIDERATIONS

In general, continuous data will be summarized using the number of observations available, mean, standard deviation (SD), median, minimum, and maximum. Categorical and ordinal data will be summarized using the count and percentage of participants.

The baseline value of efficacy parameters is defined as the last available value before randomization and prior to the first dose of study medication unless below eDiary data (WI-NRS, skin Pain-NRS and Sleep-NRS) score or otherwise specified.

The baseline for weekly average WI-NRS (skin Pain-NRS and Sleep-NRS) score is defined as the average of daily non-missing scores obtained during the 7 days prior to randomization.

The baseline value of the other parameters is defined as the last available value prior to the first dose of investigational medicinal product (IMP) if the participant is treated, or the last available value up to randomization if the participant is not exposed to IMP.

#### *Observation period*

The observation period will be divided into 4 segments:

- The **pre-treatment period** is defined as the period up to first IMP administration.
- The **treatment-emergent (TE) period** is defined as the period from the first IMP administration to the last IMP administration + 98 days. The treatment-emergent period includes the following 2 periods:
  - The **on-treatment period** is defined as the period from the first IMP administration to the last administration of the IMP + 14 days
  - The **residual treatment period** is defined as the period from the end of the on-treatment period to the end of the treatment-emergent period.
- The **post-treatment period** is defined as the period from the end of the treatment-emergent period.

The on-study observation period is defined as the time from start of intervention until the end of the study defined as the status date collected on e-CRF page “Completion of End of Study”.

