**Table 7 - Safety analyses**

Endpoint	Statistical analysis methods
Percentage of participants experiencing TEAEs or SAEs from baseline through Week 24	
Adverse event incidence tables will present by SOC (sorted by internationally agreed order), and PT sorted in alphabetical order for each treatment group, the number (n) and percentage (%) of participants experiencing an AE. Multiple occurrences of the same event in the same participant will be counted only once in the tables within a treatment phase. The denominator for computation of percentages is the safety population within each treatment group.
 
Proportion of participants with at least one TEAE, treatment emergent SAE, TEAE leading to death, and TEAE leading to permanent treatment discontinuation will be tabulated by treatment group. In addition TEAEs will be described according to maximum intensity and relation to the study intervention. Serious AEs and AEs leading to study discontinuation that occur outside the treatment-emergent period will be summarized separately.

AE: adverse event; PT: preferred term; SOC: system organ class; SAE: serious adverse event; TEAE: treatment-emergent adverse event

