

To demonstrate efficacy of dupilumab on skin lesions of PN.

	

Proportion of participants with Investigator's Global Assessment 0 or 1 score for PN-Stage (IGA PN-S) at Week 24 [Key secondary endpoint].

Proportion of participants with IGA PN-S 0 or 1 score at Week 12.

Proportion of participants with IGA PN-S 0 or 1 score at Week 8c.

Proportion of participants with IGA PN-S 0 or 1 score at Week 4c.

Change from baseline in IGA PN-S score at Week 24.

Change from baseline in IGA PN-S score at Week 12.

Change from baseline in IGA PN-S score at Week 8.

Change from baseline in IGA PN-S score at Week 4.

Proportion of participants with Investigator's Global Assessment 0 or 1 score for PN-Activity (IGA PN-A) at Week 24.

Proportion of participants with IGA PN-A 0 or 1 score at Week 12.

Proportion of participants with IGA PN-A 0 or 1 score at Week 8.

Proportion of participants with IGA PN-A 0 or 1 score at Week 4.

To demonstrate efficacy of dupilumab on both itch as well as skin lesions within the same participant

	

Proportion of participants with both an improvement (reduction) in WI-NRS by <math>\geq 4</math> from baseline to Week 24 and an IGA PN-S 0 or 1 score at Week 24 (key secondary endpoint for US and US reference countries only)

To demonstrate the improvement in health-related quality of life (HRQoL).

	

Change from baseline in HRQoL, as measured by Dermatology Life Quality Index (DLQI) to Week 24.

Objectives	Endpoints

 
• To evaluate safety outcome measures.
 
• To evaluate immunogenicity of dupilumab.
 
	
 
• Change from baseline in HRQoL, as measured by DLQI to Week 12.
 
• Percentage of participants experiencing treatment-emergent adverse events (TEAEs) or serious adverse events (SAEs) from baseline through Week 24.
 
• Incidence of treatment-emergent antidrug antibodies (ADA) against dupilumab over time.
 

Tertiary/exploratory	

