## 4.5 TERTIARY/EXPLORATORY ENDPOINT(S) ANALYSIS

### 4.5.1 Definition of endpoint(s)

The exploratory endpoints are as follows:

- Use of high potency or superpotent TCS rescue medication through Week 24
- Use of systemic immunosuppressant through Week 24, constituting treatment failure
- Change from baseline in Hospital Anxiety and Depression Scale (HADS) total score to Week 24
- Change from baseline in EQ-5D-5L Single Index score to Week 24

- Change from baseline in EQ-5D visual analog scale (VAS) to Week 24
- Change from baseline in skin Pain-NRS to Week 4, Week 8, Week 12, and Week 24, respectively
- Change from baseline in Sleep-NRS to Week 4, Week 8, Week 12, and Week 24, respectively
- Missed school/work days through Week 24
- Incidence of skin-infection TEAEs (excluding herpetic infections) through Week 24
- Proportion of participants who achieve  $\geq 75\%$  healed lesions from PAS at Week 4, Week 8, Week 12, and Week 24, respectively
- Change from baseline in exact number of lesions in representative area (as determined from PAS) at Week 4, Week 8, Week 12, and Week 24, respectively
- Change from baseline in Participant Global Impression of Severity (PGIS) of PN to Week 4, Week 8, Week 12, and Week 24 respectively
- Proportion of participants with PGIS score of “none” at Week 4, Week 8, Week 12, and Week 24 respectively
- Proportion of participants with PGIS score of “none” or “mild” at Week 4, Week 8, Week 12, and Week 24 respectively
- Participant Global Impression of Change (PGIC) of PN at Week 4, Week 8, Week 12, and Week 24, respectively
- Proportion of participants with PGIC score of “very much better” at Week 4, Week 8, Week 12, and Week 24 respectively
- Proportion of participants with PGIC score of “very much better” or “moderately better” at Week 4, Week 8, Week 12, and Week 24 respectively

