#### **4.7.2 Adverse events**

##### **General common rules for adverse events**

All adverse events (AEs) will be coded to a lower-level term (LLT), preferred term (PT), high-level term (HLT), high-level group term (HLGT), and associated primary system organ class (SOC) using the Medical Dictionary for Regulatory Activities (MedDRA) version currently in effect at Sanofi at the time of database lock.

The AEs will be analyzed in the following 3 categories:

- Pre-treatment AEs: AEs that developed, worsened or became serious during the pre-treatment period.

- Treatment-emergent adverse events (TEAE)s: AEs that developed, worsened or became serious during the treatment-emergent period
- Post-treatment AEs: AEs that developed, worsened or became serious during the post-treatment period

Similarly, the deaths will be analyzed in the pre-treatment, treatment-emergent and post-treatment periods.

The primary focus of AE reporting will be on TEAEs. Pre-treatment and post-treatment AEs will be described separately.

An AE with incomplete or missing date/time of onset (occurrence, worsening, or becoming serious) will be classified as a TEAE unless there is definitive information to determine it is a pre-treatment or a post-treatment AE.

If the assessment of the relationship to IMP is missing for an AE, this AE will be assumed as related to IMP. If the severity is missing for 1 of the treatment-emergent occurrences of an AE, the severity will be imputed with the maximal severity of the other occurrences. If the severity is missing for all the occurrences, the severity will be left as missing.

Multiple occurrences of the same event in the same participant will be counted only once in the tables within a treatment phase.

The AE tables will be sorted as indicated in [Table 6](#).

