## **Analysis of all adverse events**

The overview of TEAE with the details below will be generated:

- Any TEAE
- Any severe TEAE
- Any treatment emergent SAE
- TEAE leading to death

- Any TEAE leading to permanent intervention discontinuation
- Any treatment emergent AESI
- Any treatment emergent other AE of interest grouping
- Any TEAE related to IMP

The AE summaries of [Table 7](#) will be generated with number (%) of participants experiencing at least one event.

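### The secondary safety endpoint stops at Week 24, but no overall TEAE or treatment-emergent SAE table does: all run to 98 days after the last dose

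*SAP*

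**What the plan says.** **Endpoint.** SAP Table 2 lists the secondary safety endpoint as "Percentage of participants experiencing treatment-emergent adverse events (TEAEs) or serious adverse events (SAEs) from baseline through Week 24". The protocol's objectives tables agree, and Protocol Table 7 (Section 9.4.2) repeats it as "Percentage of participants experiencing TEAEs or SAEs from baseline through Week 24".

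**Protocol method.** Beside that endpoint, Protocol Table 7 plans AE incidence tables and the proportions with at least one TEAE and with a treatment-emergent SAE. It gives no Week 24 cut-off. It adds: "Serious AEs and AEs leading to study discontinuation that occur outside the treatment-emergent period will be summarized separately".

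**SAP window.** SAP 4.1 (Observation period) defines the treatment-emergent period as "the period from the first IMP administration to the last IMP administration + 98 days". SAP 4.7.2 defines TEAEs as "AEs that developed, worsened or became serious during the treatment-emergent period" and adds: "Pre-treatment and post-treatment AEs will be described separately".

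**SAP tables.** The AE summaries in SAP Table 7 "will be generated with number (%) of participants experiencing at least one event". Neither the TEAE overview nor any TEAE or treatment-emergent SAE row of that table mentions Week 24.

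**Where Week 24 does appear for adverse events.** There are two places. One is the exploratory endpoint in SAP 4.5.1, "Incidence of skin-infection TEAEs (excluding herpetic infections) through Week 24". The other is the optional Kaplan-Meier estimates for specific AE groupings in SAP 4.7.2.

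**The concern.** An endpoint that names a time window needs an analysis over that window. Here the endpoint stops at Week 24, while the tables that would be read as its result follow a period tied to each participant's last dose. For most participants that period is longer than 24 weeks, and for early discontinuers it can be shorter. Someone who takes the overall TEAE percentage in the study report as the Week 24 result would be reading a different quantity. The stake is the meaning of a descriptive percentage. No test or efficacy claim depends on it.

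**Working it through.** The plan gives no figure to reproduce, so the check is day arithmetic followed by a search for any planned output that matches the endpoint.

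**Inputs**
- Last planned dose: Week 22 (Protocol 1.3, Schedule of Activities).
- Safety days counted from first dose, with Week 24 targeted at Day 169 and Week 36 at Day 253 (SAP 5.4, Table 12).
- Treatment-emergent period ends 98 days after last dose; on-treatment period ends 14 days after last dose (SAP 4.1).

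**Step 1: a full course of treatment.** With day = 1 + 7 × week:
- last dose: 1 + 7 × 22 = Day 155
- Week 24: 1 + 7 × 24 = Day 169
- end of treatment-emergent period: 155 + 98 = Day 253
- excess over the endpoint window: 253 − 169 = 84 days, or 12 weeks

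**Step 2: other last doses.** For a last dose at week w, the treatment-emergent end minus Week 24 is (1 + 7w + 98) − 169 = 7w − 70 days.

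| Last dose | End of treatment-emergent period | Relative to Day 169 |
|---|---|---|
| Week 22 | Day 253 | +84 |
| Week 16 | Day 211 | +42 |
| Week 12 | Day 183 | +14 |
| Week 10 | Day 169 | 0 |
| Week 8 | Day 155 | −14 |
| Week 4 | Day 127 | −42 |
| Day 1 only | Day 99 | −70 |

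On the nominal schedule the two windows coincide only for a last dose at Week 10. With a last dose at Week 8 (Day 57), an SAE on Days 156 to 169 lies within 24 weeks but outside the treatment-emergent period.

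**Step 3: does another provision supply the Week 24 cut?**
- Both documents count repeat events once per treatment phase. That is a counting rule and sets no time limit.
- The on-treatment period ends on 155 + 14 = Day 169 for a full course, which would match. No AE table uses it; SAP 4.7.3.1 applies it to quantitative laboratory, vital-sign and ECG summaries.
- The Week 24 Kaplan-Meier estimates are optional and cover specific groupings only. The skin-infection endpoint covers one event type.
- For each AESI and selected grouping, SAP 4.7.2 counts serious events whatever their treatment-emergent status. No overall table does so.

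None of these gives an overall TEAE or SAE percentage through Week 24.

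**Step 4: what the primary lock adds.** SAP 4.9 locks the database once every participant has finished the 24-week phase and bases the study report on it. It then updates the database at study end to bring in post-treatment follow-up. Two readings are open:
- Events after Week 24 already recorded at the lock enter the report tables. A full-course participant then contributes between 0 and 84 days beyond Week 24, depending on enrolment date.
- Post-treatment follow-up enters only at the later update. The tables at the lock would then end near Week 24 for most participants.

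The SAP does not choose between them, and the enrolment duration is not stated, so the unevenness under the first reading cannot be sized.

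**The case against.** The strongest reply is that the SAP does what the protocol asked. Protocol Table 7 sets this endpoint beside AE incidence tables and treatment-emergent SAEs, with events outside the period summarized separately. On that view the words about Week 24 are a loose label, and rewording the endpoint would cure the mismatch. The window also fits the 12-week follow-up, captures more events for those who complete treatment, and is the same in both arms. SAP 4.7 makes safety descriptive, with no testing.

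Most of this stands. The window is not an error, and the mismatch starts in the protocol. But the endpoint carries the same Week 24 limit throughout both documents, and the SAP applies that limit to skin infections, so the words cannot be dismissed as a label. Rewording would restore consistency but give up the fixed-window quantity that was named.

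The SAE point is narrow. Read literally, the endpoint covers all SAEs through Week 24, but the protocol's method tabulates treatment-emergent ones. A difference arises only when the last dose is before Week 10, follow-up continues, and the SAE falls after the treatment-emergent period but by Day 169. Such events are still reported separately. A reader might infer that SAEs go unreported; the documents do not support that.

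A reader might also infer that the report's percentages necessarily mix unequal follow-up. SAP 4.9 leaves that open.

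**Conclusion.** The mismatch is established from the text. A named secondary safety endpoint has no planned overall analysis over its own window. On the nominal schedule the tables run 84 days past Week 24 for a full course and stop short of Week 24 when the last dose precedes Week 10. The consequence is limited to what a descriptive percentage means. The correction is worth making because it is simple and restores the match with the endpoint.

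Three stronger conclusions are not supported:
- **Between-arm bias.** Both arms share the window and the lock, and nothing in the documents shows a distortion of the comparison.
- **A stated inflation of incidence.** The documents give no AE rates and no time pattern, so any percentage would rest on assumed inputs.
- **Inflated exposure-adjusted rates.** SAP 4.7.2 does not name one denominator. SAP 4.7.1 defines exposure to last dose + 14 days, but SAP 4.7.2 also speaks of exposure at risk, which can be read as time over the treatment-emergent window. This wording needs clarifying; it is not a demonstrated error.

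**What to change.** 1. In SAP 4.7.2, add one overall TEAE/SAE summary restricted to onset on or before Week 24 (Day 169), and name it as the analysis of this endpoint.
2. State whether SAEs after the end of the treatment-emergent period but by Week 24 count in that summary, and reconcile the endpoint wording with the method column of Protocol Table 7.
3. Keep the treatment-emergent-period tables beside it, with a footnote saying how far follow-up extends at the primary lock and whether events after Week 24 are included.

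The cost is one extra table and one footnote, from onset dates already collected. No new data are needed, and the existing safety tables remain.

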### 1.3 SCHEDULE OF ACTIVITIES (SOA)

Procedure	Screening (2 to 4 weeks before Day 1)	Intervention period (Weeks)					Follow-up (12 weeks)	Notes
		0 (Day 1)	4	8	12	24		
Visit	1	2 a	3	4	5	6 b (EOT)	7 (EOS)	Visit window: ±3 days for Visits 3, 4, 5, 6, and 7.
Screening and baseline								
Informed consent	X							Separate consent to be obtained for optional procedures (DNA and RNA sampling, and serum/plasma sampling for archival; HIV test if specific consent locally required).
Medical history	X							
Prior and concomitant medication	X	X	X	X	X	X	X	Concomitant medication will be collected throughout the study.
Demography	X							
Inclusion and exclusion criteria	X	X						
Hepatitis c , HIV serology, TB test	X							HBs Ag, HBs Ab, HBc Ab, HCV Ab, HIV screen (Anti-HIV-1 and HIV-2 antibodies), TB test (performed locally if required and results noted in the eCRF).
Randomization		X						
Study interventiond								
Dispense or download e-diary	X	X	X	X	X	X	X	Device will be dispensed at Screening (including instructions for use). At EOS, the e-diary will be downloaded and returned to the site.
Participant e-diary training	X	X						
Call IVRS/IWRS	X	X	X	X	X	X	X	At screening visit, IVRS/IWRS will be called after medical history check.

Procedure	Screening (2 to 4 weeks before Day 1)	Intervention period (Weeks)					Follow-up (12 weeks)	Notes
		0 (Day 1)	4	8	12	24		
Visit	1	2 a	3	4	5	6 b (EOT)	7 (EOS)	Visit window: $\pm$ 3 days for Visits 3, 4, 5, 6, and 7.
IMP administration		X	X	X	X			IMP administration Q2W ( $\pm$ 3 days) from Week 0 until Week 22. Between visits, the participants will self-inject IMP at home or may choose to have injections administered at home by a caregiver or at the study site.
Safetyd								
Physical examination	X	X				X	X	Including skin (full body skin exam), nasal cavities, eyes, ears, respiratory, cardiovascular, gastrointestinal, neurological, lymphatic, and musculoskeletal systems.
Vital signs	X	X	X	X	X	X	X	Including SBP and DBP (mmHg), pulse rate (beats per minute), body temperature (°C), and respiratory rate. Body weight will be recorded at Visits 1, 6, and 7 only. Height will be recorded at Visit 1 only.
12-lead ECG	X					X		Locally collected and read.

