### 6.1 STUDY INTERVENTION(S) ADMINISTERED

**Table 2 - Overview of study interventions administered**

ARM name	Dupilumab	Placebo
Intervention name	Dupilumab 300 mg	Placebo matching dupilumab 300 mg
Type	Biological/Vaccine	Other
Dose formulation	A 150 mg/mL dupilumab solution in a pre-filled syringe to deliver 300 mg in 2 mL	Identical formulation to the active 300 mg formulation without dupilumab, in a pre-filled syringe to deliver placebo in 2 mL
Unit dose strength(s)	300 mg	0 mg (placebo)
Dosage level(s)	300 mg every 14 ±3 days after an initial loading dose of 600 mg	0 mg every 14 ±3 days with a loading dose of 0 mg
Route of administration	Subcutaneous a	Subcutaneous a
IMP and NIMP	IMP	IMP
Packaging and labeling	One glass pre-filled syringe packed in a patient kit box. Both the glass pre-filled syringe and the box will be labeled as required per country requirement.	One glass pre-filled syringe packed in a patient kit box. Both glass pre-filled the syringe and the box will be labeled as required per country requirement

a Subcutaneous injection sites should alternate between the upper thighs, 4 quadrants of the abdomen or the upper arms, so that the same site is not injected twice during consecutive administrations. Injection in the upper arms can only be done by a trained person (parent/legally authorized representative/caregiver trained by Investigator or Delegate) or health care professional but not the participant themselves.  
IMP: investigational medicinal product; NIMP: noninvestigational medicinal product.

The Investigator or delegate will train the patient (or caregiver) how to prepare and inject IMP at Visit 2. He/she will inject the first of the two injections. The participant (or caregiver) will perform the second injection under the supervision of the Investigator or delegate. Patient should also be trained by the site staff to recognize potential signs and symptoms of hypersensitivity reaction in order to self-monitor at home for at least 30 minutes (or longer per country specific or local site-specific requirements) following injection. In case of hypersensitivity symptoms the patient should contact healthcare provider/emergency. The training must be documented in the participant's study file.

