- ECG variables: heart rate, PR, QRS, QT, and QTcF intervals after 10 minutes of rest in the supine position. Data are locally collected and read at screening (V1) and Week 24 (V6).

Data below the lower limit of quantitation/detection limit (LLOQ) will be replaced by half of the LLOQ, data above the upper limit of quantification will be replaced by ULOQ value.

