### **Quantitative analyses**

For all laboratory variables, vital signs and ECG variables above, descriptive statistics for results and changes from baseline will be provided for each analysis window, the last value and the worst value during the on-treatment period. These analyses will be performed using central measurements only (when available) for laboratory variables.

For all parameters, mean changes from baseline with the corresponding standard error will be plotted over time.

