### ***Safety assessment***

For the safety assessment, the reference date for the derivation of relative days of events or findings will be the date of first IMP administration. Selected safety variables will be summarized by the analysis window define in [Table 12](#) for the by visit descriptive analysis. All available values from central lab will be assigned to the appropriate visit window. In the event of multiple measurements of the same test in the same window, the one closest to the targeted visit date will be used for the by-visit summary. If they are at the same number of days away from the target day, the latest one will be used. For procedures planned on Visit 2, if it is done on the same date as the first IMP injection but the performance time is missing, it will belong to Visit 2 time window.

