**Table 12 - Time window for safety endpoints**

Visit	Target Day	Time windows for							
		Vital signs	Hematology, biochemistry	Urinalysis	CD4 T cell count and HIV test	Serum Pregnancy test	Urine Pregnancy test	Physical examination	ECG
Visit 1 (Week -4 to -2)	<1	<-14	<-14	<-14	1-	<-14		<-14	1-
Visit 2 (Week 0)	1	-14-1-	-14-1-	-14-1-			-14-1-	-14-1-	
Visit 3 (Week 4)	29	1 + -42	1 + -42	1 + -42			1 + -42		
Visit 4 (Week 8)	57	43-70	43-70	43-70			43-70		
Visit 5 (Week 12)	85	71-126	71-126	71-126			71-126		
Visit 6 (Week 24)	169	127-210	127-210	>126	1 +		127-210	1 + -210	1 +
Visit 7 (Week 36)	253	>210	>210				>210	>210	

1-: up to 1st dose date/time; 1+: after 1st dose date/time;

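### A protocol-compliant Week 24 visit can fall after last dose + 14 days and so be left out of the SAP's last and worst on-treatment value summaries

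*SAP*

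**What the plan says.** **The cut-off.** In SAP 4.1 (Observation period) the on-treatment period "is defined as the period from the first IMP administration to the last administration of the IMP + 14 days". What follows, up to last IMP + 98 days, is the residual treatment period.

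**What uses it.** For all laboratory, vital-sign and ECG variables, SAP 4.7.3.1 (Quantitative analyses) asks for descriptive statistics by analysis window and also for "the last value and the worst value during the on-treatment period".

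**Dosing and visits.** Protocol 1.3 schedules IMP every two weeks "from Week 0 until Week 22", with a 3-day tolerance. Protocol Table 2 gives the regimen as "300 mg every 14 ±3 days after an initial loading dose of 600 mg". The visit tolerance is "Visit window: ±3 days for Visits 3, 4, 5, 6, and 7". SAP Table 12 sets the target day: "Visit 6 (Week 24) 169". For safety data, "the reference date for the derivation of relative days of events or findings will be the date of first IMP administration".

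**What is measured when.** Protocol 1.3 and SAP 4.7.3.1 schedule the ECG at screening and Week 24 only. Body weight is recorded at Visits 1, 6 and 7 only. No site visit is scheduled between Week 12 and Week 24.

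No rule in the SAP assigns the Week 24/EOT visit to the on-treatment period.

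**The concern.** The cut-off falls exactly on the target day of the visit meant to supply the end-of-treatment measurement, so it leaves no room for the visit tolerance that the protocol grants. Whether a completer's Week 24 values count as on-treatment then depends on a few days of scheduling.

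Three things happen in the rows concerned:

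- **Laboratory and vital signs.** The last scheduled on-treatment value becomes the Week 12 one, so a single label pools Week 12 and Week 24 values. The scheduled values behind the worst value then cover only the first half of treatment.
- **ECG.** The participant has no scheduled on-treatment recording, and the denominator shrinks.
- **Body weight.** The same applies, since no scheduled post-baseline weight precedes Visit 6.

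Elsewhere the SAP does allow for late Week 24 data. The eDiary window for Week 24 runs to Day 172 (Table 10), time-to-event censoring is at Day 172 (4.4.2), and exposure has a category up to 24 weeks + 3 days (4.7.1).

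**Working it through.** **Inputs.** First dose = Day 1 (SAP 5.4, Safety assessment). Last planned dose at Week 22, tolerance ±3 days (Protocol 1.3). Visit 6 at Week 24, tolerance ±3 days (Protocol 1.3). On-treatment end = last dose + 14 days (SAP 4.1). Assumption: the dose tolerance is taken around the nominal day and does not accumulate from one dose to the next.

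**Reproducing the SAP's figure.** Week 24 target = 1 + 24 × 7 = 169, which matches SAP Table 12.

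**Key days.**
- Last planned dose: 1 + 22 × 7 = 155; with tolerance, 152 to 158.
- On-treatment end after an on-schedule last dose: 155 + 14 = 169.
- Visit 6 in window: 169 − 3 = 166 to 169 + 3 = 172.
- Week 12 target: 1 + 12 × 7 = 85.

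**When a visit is lost.** Let d be the dose offset from Day 155 and v the visit offset from Day 169, each from −3 to +3. The visit is lost when 169 + v > 155 + d + 14, that is, when v > d. Lateness of the visit matters only relative to the dose.

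| Last dose (day) | On-treatment ends | In-window visit days lost |
|---|---|---|
| 152 | 166 | 6 of 7 |
| 153 | 167 | 5 of 7 |
| 154 | 168 | 4 of 7 |
| 155 | 169 | 3 of 7 (Days 170, 171, 172) |
| 156 | 170 | 2 of 7 |
| 157 | 171 | 1 of 7 |
| 158 | 172 | 0 of 7 |

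Total: 6 + 5 + 4 + 3 + 2 + 1 + 0 = 21 of 7 × 7 = 49 combinations (43%). This counts calendar combinations. The documents give no distribution of visit or dose timing.

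**Size of extension needed.** The longest in-window gap from dose to visit is 172 − 152 = 20 days.
- Last dose + 17: lost when v > d + 3, which is 3 + 2 + 1 = 6 of 49.
- Last dose + 20: lost when v > d + 6, which is 0 of 49.

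**The case against.** **The data stay in the safety analysis.** This stands, and it sets the size of the point. SAP 4.7 makes safety analyses descriptive, with no testing. The by-window tables keep a late visit: in SAP Table 12 the Visit 6 window is Days 127 to 210 for vital signs, haematology and biochemistry, after Day 126 for urinalysis, and any time after first dose for ECG. The PCSA and liver analyses and TEAEs use the treatment-emergent period, to last IMP + 98 days. A reader might infer that end-of-treatment ECGs are lost from the safety evaluation; the documents do not support that.

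**The effect is conditional.** This also stands. An equally late Week 22 dose keeps a late visit. Unscheduled measurements count toward the last on-treatment value (SAP 5.4, Unscheduled visits), so an unscheduled ECG or laboratory test could fill the gap.

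**Fourteen days is a coherent convention.** It equals one dosing interval, matches the exposure definition (SAP 4.7.1), and matches one of the two concomitant-medication summaries (SAP 5.3). That is a good reason to leave those definitions alone. It does not make the cut-off suitable for rows that need the end-of-treatment visit.

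**Participants who missed doses.** A reader might add those withdrawn after missing more than two consecutive doses, whose termination visit falls about 3 × 14 = 42 days after the last dose. They are off treatment by then, and leaving that visit out is what the definition should do.

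**Conclusion.** The point holds and is minor. When Visit 6 is later against its target than the last dose was against its own, a protocol-compliant visit is excluded from the last-value and worst-value on-treatment rows of SAP 4.7.3.1. For that participant the last scheduled laboratory or vital-sign value is then the Week 12 one (if Visit 5 took place), and there is no scheduled on-treatment ECG or body weight. The loss ranges from 0 of 7 in-window visit days after a Day 158 dose, through 3 of 7 after Day 155, to 6 of 7 after Day 152.

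It is tempting to read 21 of 49 as about 43% of completers, and to turn that into a number of participants. That would require dose and visit days to be evenly and independently spread over their windows and, for a count, a number of completers. The documents supply neither. If doses and visits are mostly on their nominal days, the loss is close to nil.

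The same rule applies to both arms, so the result is mislabelled or thinner rows, with no evident bias between arms. No efficacy, PCSA, liver or TEAE result changes.

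**What to change.** For the last-value and worst-value summaries in SAP 4.7.3.1 only, define the end of the on-treatment period as the later of last IMP + 14 days and the Visit 6/EOT date, capped at last IMP + 20 days (14 + 3 for the dose tolerance + 3 for the visit tolerance):

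end = min( max(last IMP + 14, Visit 6/EOT date), last IMP + 20 ).

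This recovers all 49 in-window combinations; a flat + 17 days would still lose 6. Leave the exposure, concomitant-medication and treatment-emergent definitions unchanged.

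The cost is one SAP sentence and one date derivation, with no change to study conduct. The downside is that a few values up to 20 − 14 = 6 days past the dosing interval are labelled on-treatment, and these rows use a slightly different cut-off from exposure. A table footnote stating the rule would make that plain.
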